6. SAFETY

6.1 Potential risks & benefits to study participants

There is no anticipated personal safety risk associated with taking part in this study. If the research team learns of important new information that might affect patient's desire to remain in the study, he or she will be told. Appropriate precautions are in place to ensure medical and personal information is kept safe through adhering to appropriate governance regulations. Participants in both the treatment arms will be allocated a wound dressing that is used for its intended licensed purpose and that is available via standard care routes. Any adverse events will be recorded, as outlined in sections below.

Apart from being allocated to a different type of wound dressing, all patients will receive the indicated clinical care they would receive when not in the trial. They will otherwise be cared for in exactly the same manner as they normally would. Participants cannot claim payments, reimbursement of expenses or any other benefits or incentives for taking part in this research.

6.2 Safety definitions

| Adverse Event (AE) | Any untoward medical occurrence in a patient or other clinical |
|--------------------|---|
| | investigation participant taking part in a trial of a medical device, which |
| | does not necessarily have to have a causal relationship with the device |
| | under investigation. |
| | |

An AE can therefore be any unfavourable and unintended sign (including an abnormal laboratory finding), symptom or disease temporally associated with the use of the device, whether or not considered related to the device.

Serious Adverse Event

A serious adverse event is any untoward medical occurrence that:

- results in death
- is life-threatening
- requires inpatient hospitalisation or prolongation of existing hospitalisation
- results in persistent or significant disability/incapacity
- consists of a congenital anomaly or birth defect.

Other 'important medical events' may also be considered serious if they jeopardise the participant or require an intervention to prevent one of the above consequences.

NOTE: The term "life-threatening" in the definition of "serious" refers to an event in which the participant was at risk of death at the time of the event; it does not refer to an event which hypothetically might have caused death if it were more severe.

6.3 Procedures for recording adverse events

All SAEs need to be reported to the sponsor/host Trust R&D within one working day of the investigator team becoming aware of them.

The relationship of each adverse event to the trial must be determined by a medically qualified individual according to the following definitions:

- **Related**: The adverse event follows a reasonable temporal sequence from intervention. It cannot reasonably be attributed to any other cause.
- **Not Related**: The adverse event is probably produced by the participant's clinical state or by other modes of therapy administered to the participant.

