Prospective, randomised controlled trial assessing MedCu copper dressing for lower limb ulcer management

(CUPRA trial, Copper dressings for Ulcers; Prospective Randomised Appraisal)

Version 1.0, dd 18 October 2024

Chief Investigator's Statement of Ownership and Content.

I, [name], confirm that this protocol is my work and is owned by me. The protocol conforms with standards outlined in the Declaration of Helsinki 1964.

Name (PRINT):____[name]______

Signature:_______

Date: _________

RESEARCH PROTOCOL SUMMARY

| TITLE: | Prospective, randomised controlled trial assessing MedCu copper dressing for lower limb management | | | |
|----------------------|---|--|--|--|
| | (CUPRA trial, Copper dressings for lower limb Ulcers; Prospective Randomised Appraisal) | | | |
| Short title: | CUPRA trial | | | |
| IRAS ethics number | 350241 | | | |
| ISRCTN trial number | To be confirmed | | | |
| Device description | CE-marked wound dressing: MedCu (by MedCu Technologies) dressings are impregnated with copper oxide microparticles. MedCu dressings are single-use wound dressing with an internal absorbent layer and one or two external non-woven, non-adherent layers. | | | |
| Study design | Prospective, randomised controlled trial | | | |
| Primary objective | To determine the relative efficacy and safety of MedCu copper-impregnated dressing versus standard of care for the management of lower limb ulcers, measured through wound status (healed vs non-healed) at 12 weeks post-baseline. | | | |
| Secondary objectives | To determine the wider efficacy and safety of MedCu copper- impregnated dressing for the management of lower limb ulcers at 4, 8 and 12 weeks post-baseline - Any adverse events related to the use of allocated dressings, and rates of (patient-requested) discontinuation of dressing Wound status (healed vs non-healed) - Quality of Life (EQ-5D-5L) - Lower limb symptoms (VEINES Sym) - Types of dressings applied in standard care arm | | | |
| Patient population | First known randomised controlled trial of MedCu dressing. Therefore pragmatic approach to allow inclusion of wider cohort of patients. Patients with lower limb ulcer of any underlying aetiology are considered for inclusion. Index wound size should be minimum of 1cm² and can be maximum of 30cm² (only one index wound per patient to be included in study). Stratification for wound size at randomisation stage. | | | |

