5. SUBJECTS

5.1 Anticipated number of research subjects

Below a summary is given for the sample size needed. The primary outcome, wound status (healed vs non-healed) is used for sample size calculation for both randomisation groups.

The sample size calculation has been performed using GPower freeware sample size calculator, based on 2x2 Chi-squared test for wound healed status. Power calculation for sample size assumes 80% power and 5% two-sided confidence interval.

Table 4: standard care vs MedCu dressing. The hypothesis is that MedCu dressing performs better to a minimum 20% (effect size 0.41) in wound healed at week 12.

Since some patients may withdraw over the course of the 12-week trial period, a 20% dropout rate is calculated into each sample size. A 1:1 allocation to the two types of dressing is applied.

Note: There will be an option to expand sample size, subject to no safety concerns after initial sample size has been reached. This then allows wound healing comparison for purer sample of 'leg ulcers' and 'foot ulcers' separately from each other. For this purpose, the same effect size will be applied. The hypothesis is that MedCu dressing performs better to a minimum 20% (effect size 0.40), requiring a sample size 66 (taking into account same 30% drop-out/withdrawal rate)

Table 4, Sample size calculations

| | Sample size calculation | | | | | |
|------------------|---|---|--|--|--|--|
| | Standard care control dressing | Intervention dressing (MedCu copper dressing) | | | | |
| Ulcer healed | 40% | 60% | | | | |
| Ulcer not healed | 60% 40% | | | | | |
| | Power beta of 80%, Alpha p-value of 0.05, effect size 0.40 Sample size required without any drop-out: 50 patients Sample size with 30% attrition rate included: 66 patients Total of 66 patients, distributed as: - 33 Patients to receive MedCu dressing - 33 Patients to receive standard care dressing | | | | | |

The CONSORT guidelines require a statement on the number of patients assessed for eligibility (Schulz, Altman & Moher 2010). The number of patients screened but who did not meet the inclusion criteria or who declined to participate will be recorded, as will any patients who are lost to follow-up (Appendix 5).

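### The two adverse-event causality classes in section 6.3 are not exhaustive: a possibly related event meets neither definition, so the related-event outcome can omit it

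*Protocol*

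**What the plan says.** Section 6.3 makes the classification compulsory: "The relationship of each adverse event to the trial must be determined by a medically qualified individual according to the following definitions". Two definitions follow.

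- Related has two conditions. The event comes at a plausible interval after the intervention, and "It cannot reasonably be attributed to any other cause". Both must be met.
- The second class, Not Related, has a single condition, which is that some other explanation is likely: "The adverse event is probably produced by the participant's clinical state or by other modes of therapy administered to the participant".

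There is no third class, and nothing says where an event goes if it meets neither definition.

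The classification bears on an outcome. The first item under the secondary objectives in the protocol summary is "Any adverse events related to the use of allocated dressings", together with patient-requested discontinuation.

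Two other provisions do not depend on causality. Section 6.1 states "Any adverse events will be recorded, as outlined in sections below", and section 6.3 states "All SAEs need to be reported to the sponsor/host Trust R&D within one working day".

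The option to enlarge the trial is, in section 5.1, "subject to no safety concerns after initial sample size has been reached". The summary makes the same option conditional on a review of safety data.

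**The concern.** A two-class causality rule works only if every event falls into one class. Here the two definitions set their thresholds at different points. Related requires that no other attribution is reasonable. Not Related requires that another cause is probable. Between reasonable and probable lies the group that a safety review most wants to see: events the dressing may have caused, where another explanation is also credible.

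The trial population makes that group relevant. Section 5.2.1 admits ulcers of any aetiology and allows contributing conditions such as diabetes, rheumatoid arthritis and peripheral vascular disease. Section 7.1 records eczema, psoriasis and other dermatitis at baseline. Section 4.3 includes compression in the advice given to both arms. Each can supply a second credible explanation for a local skin reaction or a worsening wound. Appendix 1 itself foresees reactions to the allocated dressing.

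At stake is how the related-event outcome can be read in what the summary calls the first known randomised trial of this dressing. A low count could mean few dressing reactions, or it could mean that uncertain reactions had no class to go into. Section 5.1.1 says participants cannot be blinded. It provides blinding for the statistical analysis but says nothing of the person who judges causality. Judgement used to fill the gap may therefore differ between arms.

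**Working it through.** The document states no figure on this point, so the main check is logical.

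**Step 1. Sort events by the strength of the other explanation.** Take an event that follows the intervention in a plausible time, so that the timing condition is met. A probable other cause is also a reasonable one, which leaves three cases.

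| Case | Other cause | Meets Related? | Meets Not Related? | Result |
|---|---|---|---|---|
| a | not reasonable | yes | no | Related |
| b | reasonable, not probable | no, because another attribution is reasonable | no, because the other cause is not probable | no class |
| c | probable | no | yes | Not Related |

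Case b is empty only if reasonable and probable mean the same thing. The protocol uses two different words and defines neither.

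**Step 2. Trace the consequence.** The summary's outcome counts events related to the allocated dressing. A case b event does not meet Related, so a literal count leaves it out. The object of the assessment also differs: section 6.3 judges relationship to the trial, while the summary counts relationship to the dressing.

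**Step 3. Express the size.** Let N be the number of events that are at least possibly related (cases a and b), g the share of these in case b, and s the share of case b events that assessors nevertheless place under Related. Then

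reported related events = N × [1 − g × (1 − s)].

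The protocol gives no value for N, g or s. The following values of g are assumed, to show the range only.

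| g (assumed) | s = 0 (literal reading) | s = 1 (all case b events called Related) |
|---|---|---|
| 10% | 1 − 0.10 = 90% | 100% |
| 30% | 1 − 0.30 = 70% | 100% |
| 50% | 1 − 0.50 = 50% | 100% |

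The result therefore depends as much on s, which the protocol leaves open, as on g. If s differs between arms, so does the capture. With g = 30% in both arms, the extremes are 70% in one and 100% in the other, for the same underlying events.

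**Step 4. Mark what is unaffected.** The adverse-event definition in section 6.2 applies whether or not an event is thought related to the device. Recording under section 6.1 and serious-event reporting under section 6.3 carry no causality condition. The raw data are intact, and only the related-event classification is at risk.

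**The case against.** The strongest reply is that the two definitions were meant as complements: either another cause is the credible attribution or it is not. On that reading the gap is loose wording, and an assessor with two boxes will tick one of them. This is a possible intention, but the text does not say it. Two assessors could read the rule differently and both be following it.

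A second reply is that much of the harm is captured elsewhere. Infection rate, ulcer size, PUSH score, leg symptoms and withdrawal for a change in management are outcomes in section 4.5.2. Appendix 1 requires the date and reason when a dressing is stopped or paused. This stands, and it limits the point to one safety item among several. That item is named only in the summary, and the lists in sections 3.2 and 4.5.2 do not repeat it.

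A third reply is that a more inclusive rule can overcount, since some case b events will have been caused by something else. This also stands. It is a reason to report all-cause events by arm beside the related ones.

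A reader might infer more than the document supports in two respects:

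- **That the rule guarantees an undercount or drives related events toward zero.** It does not. With no default, an assessor may place some or all case b events under Related, and then little or nothing is lost.
- **That the related-event count decides whether the trial is expanded.** Neither the summary nor section 5.1 limits the safety review to related events, and all adverse events and serious events are available to it.

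**Conclusion.** The concern holds as a defect in the stated rule. Section 6.3 obliges assessors to use two definitions that leave possibly related events without a class and without a default. Read literally, the related-event outcome in the summary omits those events. Read loosely, it depends on unguided individual judgement in a trial whose participants know their dressing.

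The direction under a literal reading is downward. The size cannot be computed, because the protocol gives no adverse-event rates and no share of uncertain events. The percentages shown above are assumptions, and any specific rate of missed reactions would be too. That the population often offers a second credible cause is a reasonable expectation from the eligibility criteria and baseline list, not a figure in the document.

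The scope is limited. The primary outcome, all-cause adverse-event recording and serious-event reporting are not affected. The correction should still be made, because it is cheap and because the classification decides what a listed safety outcome counts.

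**What to change.** In section 6.3 and on the adverse-event form:

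1. Make the classes exhaustive. Define Related as a reasonable possibility that the allocated dressing caused or contributed to the event, with everything else Not Related. Alternatively, add a possibly related class and state that it counts as related.
2. Assess relationship to the allocated dressing, not to the trial, so that section 6.3 matches the outcome in the summary.
3. Apply the same rule in the same way to the copper and standard care arms.
4. Report all-cause adverse events by arm alongside related ones, and state that the safety review before any expansion uses both.

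The cost is a few lines of text and a form change, with no effect on sample size or visits. The downside is that the reported related-event rate may be somewhat higher and may include some events the dressing did not cause. The by-arm comparison of all-cause events helps to interpret that.

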7. STATISTICAL CONSIDERATION AND DATA ANALYSIS PLAN

7.1 Analysis of baseline characteristics

To determine the demographics and characteristics of the patients, the following baseline data will be collated:

Patient details

- Age
- Sex
- Height, Weight, BMI

- Smoking status
- Postcode (deprivation score)
- Mobility status: does not walk / walks with assistance (stick/frame) / walks without assistance.

Medical history and status:

- Significant comorbidities, including CEAP Clinical score, Peripheral Arterial Disease, Diabetes (type I, type II, +/- neuropathy), Heart failure, Eczema, Psoriasis, Other dermatitis, Cancer
- Any previous lower limb ulcers (within last 2 years).

Index lower limb and ulcer status

- ABPI (within last 3 months), or reason for non-measurement
- Ulcer location: above malleolar region (ie leg) / spanning malleolar region (ie ankle) / below malleolar region (ie foot)
- Chronicity of ulcer (in weeks)
- Ulcer size (PUSH score / digital Healthy io App)
- If lower limb ulcer healed at week 4 and/or week 8, status of index location at week 12 (ie any recurrence of ulcer?)

Dressing care characteristics

- Frequency of care (change of dressing: per week.
- 'Prescribed' compression bandaging: yes / no
- Which specific dressing used on wound?

Any differences in distribution will be established with Chi-squared test or ANOVA as indicated.

7.2 Primary outcome statistics

The primary objective for this pilot study wound healed status at week 12.

For comparative performance (superiority) analysis, any statistically significant difference (p-value < 0.05) between the two treatment arms will be determined with Chi-squared test.

Analyses will be performed on a per protocol basis, with only those participants that data is available for included in the analysis. Data will first be collated in Microsoft Excel, followed by analyses performed using SPSS v20.

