3. STUDY HYPOTHESIS

3.1 Primary objective

To determine the efficacy of MedCu copper oxide impregnated wound dressing for the management of lower limb ulcers, measured through wound status (healed vs non-healed) at 12 weeks post-baseline

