5.3 Early withdrawal of subjects

Patients have the right to withdraw from the trial at any time and without giving any reason. If a patient withdraws from the trial, any and all information gathered prior to the withdrawal will be included in the analysis, though no further data collection will occur. If a patient does not attend planned follow-up appointments then two more attempts will be made to contact the patient regarding the study. If still no contact can be made then the patient is deemed lost to follow-up and any collected study data will be retained. Appendix 2, INTERVENTION DEVIATION AND LEG ULCER INFECTION, covers study withdrawals in more detail.

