APPENDIX 1. INTERVENTION DEVIATION AND LOWER LIMB ULCER INFECTION

There may be incidences where a participant may either:

- Develop a reaction to the allocated dressing.
- Becomes completely non-compliant (possibly due to allocated dressing being uncomfortable, or eg hospital admission)
- Improve to such an extent that allocated dressing is no longer indicated.

In such instances the patient and/or clinician can opt to stop or pause treatment with the dressing in question. If this occurs, this needs to be recorded (date and reason), and the decision can then be made to either:

- Discontinuation of intended dressing due to improvement in symptoms (including wound healed). Participant will still continue to be assessed as per planned dates and timepoints.
- Change over to an alternative dressing that is not the originally allocated type. This is allowed but only if there are clinical indications to do so or at patient request if they cannot tolerate the allocated dressing. Patient can later in trial period be transferred back to original allocated bandage type if required.
- Pausing or discontinuation of wound dressing when not clinically indicated. Even if lower limb ulcer persists and patient no longer wears allocated dressing, they can still continue in the trial if they wish. Outcome measures will continue to be recorded as per planned dates and time points.
- Pause or discontinuation due to adverse event. Patient can remain in trial provided they are capable to continue with follow-up schedule and completion of outcome measures. If not possible, see next point regarding 'Withdraw patient from study'.
- Withdraw patient from study.
 - o At the request of the patient
 - For clinical reasons, eg if the leg ulcer has deteriorated to such an extent that emergency surgical or medical intervention is required which means return to use of any dressing in reasonable time frame (within time to next trial follow-up visit) is not feasible. In this case, this needs to be reported as a (Serious) Adverse Event if discontinuation is due to deterioration of the index wound or index leg only.

When overall trial participation for a patient is finished early, the participant will still be asked to complete the relevant questionnaires (provided they have capacity to do so):

- Week 4, week 8 and week 12 VEINES Sym questionnaire
- Week 12 EQ5D5L QoL questionnaire

Infection and use of antibiotics during trial

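### The primary superiority test uses only a per-protocol, available-data set, so who is analysed depends on events after randomisation that are linked to healing

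*Protocol*

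**What the plan says.** Protocol section 3.1 sets the primary endpoint, "measured through wound status (healed vs non-healed) at 12 weeks post-baseline". Section 7.2 sets the test: "For comparative performance (superiority) analysis, any statistically significant difference (p-value < 0.05) between the two treatment arms will be determined with Chi-squared test". It then sets the population: "Analyses will be performed on a per protocol basis, with only those participants that data is available for included in the analysis". No other analysis set is named in the protocol, and nothing beyond data availability says what per protocol means.

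Appendix 1 lists the events that can end or interrupt use of the allocated dressing. They include a reaction, complete non-compliance, and improvement: "Improve to such an extent that allocated dressing is no longer indicated". Patients may switch dressing, pause or stop and remain in follow-up: "Even if lower limb ulcer persists and patient no longer wears allocated dressing, they can still continue in the trial if they wish". Appendix 1 says that outcomes continue to be recorded for patients who stop in this way, and that those who stop because of improvement are still assessed.

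Withdrawal is different. Appendix 1 gives ulcer deterioration needing emergency intervention as one reason. Section 5.3 says that "any and all information gathered prior to the withdrawal will be included in the analysis", but that nothing more is collected afterwards. For patients who finish early, Appendix 1 asks only for the VEINES Sym and EQ-5D-5L questionnaires. Neither place provides a week-12 wound status for a withdrawn patient.

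**The concern.** A superiority claim rests on comparing the groups that randomisation created. If membership of the analysed groups depends on what happened after randomisation, and what happened is related to healing, the groups are no longer guaranteed to be comparable.

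Both readings of section 7.2 have this feature. Under a strict reading, patients who left their allocated dressing could be removed, some because they improved and some because they did not tolerate it. Under the data-available reading, patients withdrawn for deterioration leave the denominator although they are very likely non-healers. The dressings look different and participants are not blinded (section 5.1.1), and the patient or clinician can decide to stop (Appendix 1). Losses that differ by arm are therefore plausible. The trial also allows for substantial attrition: Table 4 plans for 30%, while the text of section 5.1 also gives 20%.

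**Working it through.** **Step 1. Who leaves the primary analysis under each reading (section 5.3, Appendix 1).**

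| Event | Week-12 wound status recorded? | Strict per protocol | Data available |
|---|---|---|---|
| Dressing stopped because of improvement, stays in trial | Yes | Could be dropped | Kept |
| Dressing switched, paused or stopped for another reason, stays in trial | Yes | Could be dropped | Kept |
| Withdrawn because the ulcer deteriorated | No | Dropped | Dropped |
| Withdrawn on request, or lost to follow-up | No | Dropped | Dropped |

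The third row applies under both readings.

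**Step 2. The plan's own attrition figure.** Table 4 starts from 50 patients and allows for 30% loss: 50 × 1.30 = 65, made even at 66, or 33 per arm. If 30% are lost, 66 × 0.70 = 46.2, so about 46 patients (23 per arm) have data. With the 20% also stated in section 5.1, 66 × 0.80 = 52.8.

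**Step 3. Effect on the observed healing rate.** Let p be the true healing rate, m_h the fraction of healers lost and m_f the fraction of non-healers lost. Then

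observed rate = p(1 − m_h) / [p(1 − m_h) + (1 − p)(1 − m_f)].

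Take p = 0.40 in both arms (the standard-care rate in Table 4, with no treatment effect) and m_h = 0 in the affected arm. The loss patterns are assumptions.

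- Moderate: one arm loses 20% of its non-healers and the other loses nobody. 0.40 / (0.40 + 0.60 × 0.80) = 0.40/0.88 = 45%, against 40%.
- Extreme: one arm's whole 30% loss is non-healers, so m_f = 0.30/0.60 = 0.50. 0.40 / (0.40 + 0.30) = 0.40/0.70 = 57%, against 40% if the other arm loses nobody or loses patients at random. The gap is 17 points, against the 20-point target.

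**Step 4. False-positive rate.** Simulation of 200,000 trials, 33 per arm, true healing 40% in both arms, Chi-squared test without continuity correction at two-sided 5%. MedCu is taken as the more affected arm; reversing the arms reverses the sign.

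| Assumed loss | Expected observed rates, MedCu vs control | Rejection |
|---|---|---|
| None | 40% vs 40% | 5.9% |
| 30% at random in both | 40% vs 40% | 5.2% |
| 30% in both, all non-healers | 57.1% vs 57.1% | 5.2% |
| 20% in both; MedCu all non-healers, control at random | 50% vs 40% | 11.5% |
| 30% MedCu, 10% control, all non-healers | 57.1% vs 44.4% | 15.2% |
| 30% in both; MedCu all non-healers, control at random | 57.1% vs 40% | 21.7% |

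With no true effect, bias appears only when the amount or kind of loss differs by arm.

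**Step 5. What missing status leaves open in one arm.** With 10 of 33 missing and 40% healed among the 23 observed (9.2 patients), the arm's rate lies between 9.2/33 = 28% and (9.2 + 10)/33 = 58%.

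**Step 6. Is counting every missing patient as not healed enough?** In the 30% vs 10% row, where all losses really are non-healers, it restores 40% vs 40% and 5.9% rejection. In the last row it gives 40% against 0.40 × 0.70 = 28%, with 18.6% rejection. It works only when the assumption behind it is true in both arms.

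**The case against.** The best defence is that section 7.2 explains its own term: the rest of the sentence speaks only of participants with data, and nothing in the protocol links a change of dressing to exclusion. Section 4.5.1 counts an ulcer as healed only once it needs no dressing, so removing everyone who stopped would remove the successes, which cannot be intended. This stands. A reader might infer that patients followed off their dressing will be discarded. The document does not say so; that follows only on the strict reading. The term still needs a definition, because the strict meaning is the conventional one.

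A reader might also infer that section 5.3 contradicts section 7.2. On the data-available reading it does not: week-4 and week-8 data from a withdrawn patient can enter the secondary analyses while a missing week-12 status cannot enter the primary test.

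Third, the documented withdrawal for deterioration is narrow, and nothing suggests that it would reach 30% of an arm. That also stands, and it makes 57% vs 40% an extreme case and not a forecast.

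Two further defences do not succeed. An unseen SAP may well hold the imputation details, and their absence here is no fault; but the protocol affirmatively names the analysis set, so a SAP would have to contradict it. And although section 7.2 calls the study a pilot, the trial is sized for a formal test: "Power calculation for sample size assumes 80% power and 5% two-sided confidence interval".

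**Conclusion.** The point holds and should be corrected before the trial is analysed. The protocol names a per-protocol, available-data set as the only set for its primary superiority test and leaves per protocol undefined. On either reading, inclusion depends on post-randomisation events that Appendix 1 links to healing.

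That conclusion rests on the text alone. The size and direction of any bias do not: they depend on loss patterns that the documents cannot supply. Under the assumed patterns with no true effect, the spurious difference runs from nil (like losses in both arms), through about 5 points (20% of non-healers lost in one arm only), to 17 points in the extreme case. It would be wrong to conclude that the trial will show a false benefit, or that bias must favour MedCu.

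**What to change.** In section 7.2:

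- Make the primary analysis all randomised participants by allocated arm, whatever dressing changes, pauses or stops occur.
- Count withdrawal for deterioration of the index ulcer as not healed.
- Handle other missing week-12 status by a prespecified method, for example multiple imputation using arm, PUSH stratum, baseline area and week-4 and week-8 status. With 33 per arm the imputation model has limited information, so sensitivity analyses are needed. Counting all missing as not healed can be one of them but should not stand alone (Step 6).
- Define per protocol and keep it as supportive only. Stopping a dressing because the ulcer healed or improved should not remove a patient from it.

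Align section 5.3 and Appendix 1 with this, and record week-12 wound status after early end of participation where the patient agrees. Rewording section 7.2 alone cannot recover a status that is never collected.

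Cost: wording in sections 7.2 and 5.3 and Appendix 1, modest extra analysis, and a small amount of extra follow-up for consenting patients who finish early. Follow-up of patients who leave their dressing but stay in the trial is already planned.
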